2.1. Eligibility Criteria

2.1.1. Inclusion Criteria

All subjects:

1. 40-70 years old
2. Male
3. BMI overweight-obese: 25.0—40 kg/m²
4. Colonoscopy within the last **three** years that found ≥ 1 adenoma
5. English speaking
6. Ambulatory, able to come to either food distribution site to pick up food and participate in clinical examinations and laboratory tests

2.1.2 Exclusion Criteria

1. Serious medical condition (e.g., cancer, heart disease, kidney disease, diabetes)
2. History of CRC, bowel resection, polyposis syndrome, or inflammatory bowel disease
3. Smoked regularly in the past year
4. Dietary restrictions substantially limiting compliance or vegetarian or Vegan diet
5. Planning on changing diet or exercise behavior in the next 6 months
6. Regular use of medication that may alter inflammation markers, insulin, glucose, or gut function (i.e. regular use of non-steroidal anti-inflammatory medication, insulin therapy, steroid therapy, or antibiotics)

2.2. Research Eligibility Evaluation

[figure not shown]
We will conduct the standard screening tests required by the ACTSI for healthy participants. A history and a physical will be performed by a clinician for all participants at the Emory ACTSI site (PA or Nurse Practitioner). Participants should be in good health. Use of medications to control blood pressure, blood lipids or other weight-related concerns is acceptable provided the participant is under a physician's care and considered in good control and the medication will not interfere with outcome measures.

2.2.1. Strategies to Recruit and Enroll Participants

Subjects eligible according to a phone interview will be invited to one of the study sites. On this visit, after receiving informed consent, the participant's height, weight, and blood pressure will be checked. All eligible consented participants will be asked to visit the Emory ACTSI site to assess their resting metabolic rate (RMR) to be used to plan meals that will facilitate a weight loss of 1-2 pounds per week (energy deficit ~500-1000 kcal/day). Once their individualized diet plan is developed participants will all undergo a one-week run-in of diet similar to the control diet. The run-in helps to standardize conditions before the baseline biomarker collection and provides some confidence in the participants' ability to adhere to the study protocol.

3. STUDY IMPLEMENTATION

Overall Study Design of Legume Pilot Trial

3.1.1. Timing of Biological Specimen Collection

At randomization, after a one week run-in period, the baseline blood and fecal samples will be collected. These same specimens will be also collected at the end of the study period, after 8 weeks. All biomarker collections will take place at the Emory ACTSI site.

3.1.2 Dietary Intervention Administration

A menu cycle will be developed with a standard set of legumes of the *Phaseolus vulgaris* species, such as navy beans, pinto beans, and kidney beans in order to limit nutrient and phytochemical differences in the legume-intervention diet. The diet will contain approximately 250g of legumes per day (~1 ½ cups cooked) provided in two pre-portioned single serving entrees (i.e. ~125g each). This level will add approximately 20 grams of total dietary fiber and 8 grams of soluble fiber per day. Adding 1 ½ cups of legumes would double the dietary fiber content of the typical American diet. The intervention diet treatment will consist of two legume-enriched pre-portioned meal entrees per day with other meal components being provided by the study participants. The control group will also receive two pre-portioned meal replacement entrees, with the other meal components provided by the study participants. All entrees will be prepared, pre-portioned and frozen at the Morehouse site and transported to the Emory site as needed. Frozen entrees will be picked up by participants weekly at the respective study sites and any uneaten entrees returned the following week and recorded. Weights will also be measured weekly at these visits. For both groups, guidance will be provided by study personnel for the meal components which are self-selected to meet participants' diet plans. Study personnel include three registered dietitians (the PI, a Co-I, and an ACTSI RD) to provide dietary guidance which will be supplemented with individualized written materials. During the first 1-2 weeks of the participants' diet treatment the study coordinator will contact them regularly to answer any questions and to provide support and encourage adherence. The consumption of ad libitum "sides" contributing to total energy intake is not controlled by the study to enable us to evaluate the role of legumes in promoting satiety and control of self-selected total food intake.

4. DATA COLLECTION AND EVALUTION

4.1 Data Collection

4.1.1 Anthropometric Measures

Body weight, height will be measured by trained personnel using procedures based on the NHANES Anthropometry Procedures Manual 63. Briefly, participants will have their body weight and height measured in light clothing without shoes on a regularly calibrated digital scale. Height will be measured in duplicate using a wall-mounted stadiometer.

4.1.2 Body Composition

Body composition will be assessed using dual energy X-ray absorptiometry (DXA) in the ACTSI at Emory University. This method uses a whole-body scanner to measure total body composition and fat content with a high degree of precision. It is safe and noninvasive with little burden to the individual. Data from the DXA scans will be used to assess longitudinal changes in body fat that accompany weight loss. This data will also allow examination of changes in fat distribution at defined regions in the body.

4.1.3. 24 Hour Diet Recall

Subjects will be asked by a trained study staff member to recall their food and beverage intake during the previous 24 hour period or the preceding day. During the week prior to randomization, two unannounced telephone 24 hour recall interviews will be conducted, one during a weekday and one on a weekend. This will be repeated again during the second week after randomization, and again during the 7th week of randomization. The interview will follow a four-stage, multiple-pass interview technique and be conducted over the phone using Nutrient Data Systems for Research (NDSR), the state of the art diet assessment and nutrient analysis

program for research. NDSR estimates total energy, macro- and micro-nutrient intake and captures intake for the entire day, specific meals, dietary patterns, or individual foods.

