1.1.2. Secondary Objectives

1. Assess whether the legume diet reduces the average daily dietary energy intake of participants compared to a controlled diet.
2. Compare satiety of the high-legume diet to the control diet using self-reported satiety questionnaires.
3. Assess the effects of the two diet treatments on fasting levels of C-reactive protein (CRP, a marker of inflammation) and total cholesterol level.
4. Evaluate the effects of the aforementioned diet treatments on markers of appetite regulation (cholecystikinin – CCK) and insulin resistance (insulin, glucose) in a meal response time course experiment.
5. Compare the effects of the high-legume and control diets on gastric emptying time and gut transit time.
6. Evaluate diet-related changes in fecal biomarkers associated with CRC risk.

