4.2. Statistical Considerations

The main endpoint of interest in this study is weight loss. There are several proposed mechanisms by which legumes are thought to promote weight loss, many of which have not been tested in a controlled setting. Due to new technology, we are now able to examine one of these proposed mechanisms—colon transit time, allowing us to directly observe a legume diet's physiologic effect. Previous studies of legume-heavy diets have shown indications that the particular type of fiber specific to legumes may increase satiety and slow gastric emptying significantly, leading patients to consume fewer calories per day, thereby promoting weight loss without intensive intervention from the study staff. Thus, we do expect to have differences in energy intake between groups. The analyses will follow the intent-to-treat principle. BMI will certainly be considered as a possible confounder. Since this is a pilot trial, doing so will be important to determine the appropriate target population for a full-scale trial and whether randomization in that protocol should be stratified by BMI. Secondary outcomes, including both the satiety hormones and glucose are expected to rise quickly in response to the test meal and then decline over the course of the next few hours as gastric emptying occurs.

In the Legume Inflammation Feeding Experiment full-feeding study, participants averaged -3.9 ± 0.4 kg over the course of four weeks⁸. Ten participants (five individuals per treatment arm) would be sufficient to detect a difference of just 1.25kg (we expect > 1 kg) in weight loss, with 80% power, assuming a standard deviation for each groups' weight loss that is slightly higher (± 0.7 kg) than seen in our prior study⁸. To account for the potential small dropout rate, we will recruit a total of 14 patients (7 per treatment arm). There are multiple secondary outcomes that we are interested in determining the appropriate sample size for when we run a full-scale study. Some of these outcomes are novel, so we are exploring the feasibility of pursuing them in a full scale study.

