Within-subject changes in end-points will be compared by paired t-test; comparisons between treatment groups by two-sample t-tests. For the time course experiments, because of the large expected individual variations in fasting levels of metabolic and appetite hormones, we intend to compute the change from baseline at each time point for each individual for all of the variables and subsequently comparing the area under the curve results⁵⁵. All data will be presented as means \pm SEM; the probability level at which differences will be considered significant will be $P < 0.05$. All analyses will be performed using the most recent version of SAS (SAS Institute, Cary, NC).

Timeline

	Mo. 1	Mo. 2	Mo. 3	Mo. 4	Mo. 5	Mo. 6	Mo. 7	Mo. 8	Mo. 9	Mo. 10	Mo. 11	Mo. 12
IRB Approval, set up	X	X										
Recruiting			X	X	X	X	X	X				
Follow-up				X	X	X	X	X	X	X		
Biomarker Analysis									X	X	X	X
Statistical Analysis											X	X
Manuscript Preparation											X	X
Report to Funding Agency												X
Draft of Subsequent R01												X

REFERENCES

1. National Center for Health Statistics (NCHS). National Health and Nutrition Examination Survey Data. 2005-2006. *US Dept. of Health and Human Services, Centers for Disease Control and Prevention*. 2007; Washington, DC.

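### The plan does not say how the two baseline and four follow-up diet recalls enter the energy-intake comparison, and gives no adjustment for baseline intake

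*Combined protocol and SAP*

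**What the plan says.** The first secondary objective (section 1.1.2) is: "Assess whether the legume diet reduces the average daily dietary energy intake of participants compared to a controlled diet".

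Section 4.1.3 sets the measurements. In the week before randomization, "two unannounced telephone 24 hour recall interviews will be conducted, one during a weekday and one on a weekend". Then: "This will be repeated again during the second week after randomization, and again during the 7th week of randomization". That makes two recalls at baseline, two in week 2 and two in week 7.

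Section 4.2 gives one general analysis rule: "Within-subject changes in end-points will be compared by paired t-test; comparisons between treatment groups by two-sample t-tests". Only the time-course experiments get a defined summary per man (change from baseline, then area under the curve). On covariates the section says "BMI will certainly be considered as a possible confounder", without a model and without mention of baseline intake.

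Section 2.2.1 adds that before baseline "participants will all undergo a one-week run-in of diet similar to the control diet".

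**The concern.** The rule in section 4.2 leaves at least six analyses open: week 2, week 7 or their mean, each as a follow-up value or as a change from baseline. All would be tested at the same 0.05 level, and the choice could be made after the data are seen.

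The choice also affects precision. A two-day mean carries much day-to-day error. A change score subtracts one such mean from another and so counts that error twice; using one follow-up week leaves half of the follow-up recalls out.

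Energy intake is the proposed route from legumes to weight loss. Section 4.2 expects the arms to differ on it and wants the secondary outcomes to inform the size of a full-scale study. An estimate that is less precise than the data allow, or chosen after the fact, serves that purpose poorly.

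**Working it through.** **The plan's own figure.** No SD, effect or power is given for energy intake. The only sample-size figure is for weight: difference 1.25 kg, SD 0.7 kg, 80% power. By the normal approximation, n = 2 × (1.960 + 0.842)² × 0.7² / 1.25² = 4.9, so 5 per arm, as stated. (An exact two-sided t-test gives about 70% power at 5 per arm; that is a separate matter.) The trial is sized for weight only.

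**Inputs.** From the documents: 2 baseline and 4 follow-up recalls (4.1.3); 7 per arm recruited, 5 per arm needed (4.2). Assumed: between-man SD sb = 300-500 kcal and day-to-day SD sw = 500-700 kcal. The model is a constant level for each man plus independent daily error.

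**Variance per man of the quantity compared**, with sb = 400 and sw = 600 as the example:

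- Single-wave change: sw²/2 + sw²/2 = 360,000
- Change to the four-recall mean: sw²/2 + sw²/4 = 270,000
- Four-recall mean, unadjusted: sb² + sw²/4 = 250,000
- Four-recall mean, ANCOVA on the baseline pair: sb² + sw²/4 − sb⁴/(sb² + sw²/2) = 250,000 − 75,294 = 174,706

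| Compared with ANCOVA | Example | Range over the SD grid |
|---|---|---|
| Single-wave change | 2.06 | 1.71-2.60 |
| Change, all four follow-up recalls | 1.55 | 1.29-1.95 |
| Four-recall mean, unadjusted | 1.43 | 1.13-2.14 |

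**Small-sample cost.** These ratios treat the ANCOVA slope as known. Estimating it inflates the expected variance by 1 + 1/(N − 4): 1.10 at N = 14 and 1.17 at N = 10. The lost degree of freedom moves the t critical value from 2.179 to 2.201, or from 2.306 to 2.365. Squared CI width therefore grows by (2.201/2.179)² × 1.10 = 1.12 at N = 14, and by (2.365/2.306)² × 1.17 = 1.23 at N = 10.

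Net of this:

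- Single-wave change: 1.5-2.3 at N = 14, 1.4-2.1 at N = 10.
- Unadjusted four-recall mean, smallest gain: 1.13/1.12 = 1.01 at N = 14, but 1.13/1.23 = 0.92 at N = 10.

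**Precision after the fix, 7 per arm.** The ANCOVA variance runs from 114,826 (sb 300, sw 500) to 246,237 (sb 500, sw 700). The standard error of the arm difference is √(2 × 1.10 × variance / 7) = 190 to 278 kcal/day. The 95% half-width is 2.201 times that: 418 to 612 kcal/day.

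**Benchmark.** Section 2.2.1 pairs 1 pound per week with about 500 kcal/day. A 1.25 kg difference over 8 weeks is 1.25/0.4536/8 = 0.344 pounds per week, or 172 kcal/day. The half-width is more than twice that.

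**The case against.** A reader might infer that the plan has chosen t-tests on two-day averages, with weeks 2 and 7 tested separately. It has not said so. Section 4.2 does not mention the recalls, and a two-sample t-test on the four-recall mean would satisfy both its wording and the objective's reference to average daily intake. What the documents show is an unspecified summary, not a chosen inefficient one.

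A reader might also infer that combining the recalls halves the variance at no cost. The halving needs the single-wave change score as comparator, the baseline covariate and the assumed SDs. Averaging the follow-up recalls without the covariate lowers a change score's variance by only 25% (270,000 against 360,000 above). And 'no cost' is true of data collection alone.

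Three further points stand:

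- The baseline recalls probably fall in the run-in on a control-like diet, so they may correlate less with later intake than the model assumes. With a common correlation ρ between two-day means, the gain over the unadjusted four-recall mean is (1 + ρ)/[(1 − ρ)(1 + 2ρ)]. That is 1.16 at ρ = 0.3 but 1.07 at ρ = 0.2, below the 1.12 cost at N = 14.
- Averaging weeks 2 and 7 targets mean intake over treatment, not late intake. This fits the stated objective, but it is a choice.
- This is a pilot sized for weight, and no analysis of these recalls will be precise at 14 men.

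None of this supplies the missing definition or removes the case for baseline adjustment.

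**Conclusion.** The point holds as a gap in specification with a cheap improvement available. The documents do not define how the six recalls are used, name only t-tests, and give no adjustment for baseline intake.

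The size of the gain depends on which t-test would have been run and on SDs that the documents do not give. It is substantial against a single-wave change score and moderate against a change score using all four follow-up recalls. Against the unadjusted four-recall mean it ranges from nothing to about twofold before the small-sample cost; after that cost, the low end is break-even with 14 men and slightly worse with 10.

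It would go too far to say that the plan's choice of test is what makes a null result uninformative. The interval remains wide after the fix, so the wording of the report matters as much as the method.

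**What to change.** Add to section 4.2, in words such as these:

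> Energy intake is the mean of each man's four post-randomization recalls (weeks 2 and 7). Arms are compared by ANCOVA with the mean of his two pre-randomization recalls as covariate. The difference is reported in kcal/day with a 95% CI. Weeks 2 and 7 are also shown descriptively. A non-significant result is reported as imprecise, not as evidence of no effect.

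A useful marker for that last sentence is whether the interval contains both 0 and −172 kcal/day.

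The change needs no new data. It costs one degree of freedom and the estimation of one slope, and it fixes the target as mean intake over treatment; a sponsor who wants late intake should say so and accept fewer recalls.

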4.1.4. Satiety and Taste Measures

Meal Appetite Rating Forms will be provided to each subject to assess appetite and satiety in response to test meals for each diet treatment. These will be completed before the time course test meal, immediately after eating the test meal and each time blood is drawn. Increased hunger and decreased satiety have been linked to decreased adiposity and weight loss, and these changes may undermine the maintenance of weight loss⁵⁰⁻⁵³.

A phone interview to assess participant satiety will be conducted two times a week for the duration of the study. These phone interviews will be performed separately from the 24 hour recall, and will be scheduled with participants in advance. This contact also will allow us to assess any gastrointestinal symptoms such as bloating, change in bowel habits and abdominal discomfort.

Two additional questionnaires will assess preferences for different types of foods and aspects of the two diets under standardized conditions. These two questionnaires will be administered twice during the study, baseline and follow-up.

4.1.5. Blood Collection

Approximately 70ml of blood will be collected from the subjects at each of two time points at randomization and at the end of the eight week diet period. Samples will be collected after an overnight fast and in the early morning. For satiety measures, 15 ml of blood will be drawn before the test meal (fasting), and 10 ml of blood at 5 time points thereafter (30, 60, 90, 120, and 180 minutes). Serum and plasma samples will be aliquoted in smaller vials and frozen at -70°C and stored for analysis at the completion of the study.

4.1.6. Blood Analyses

Approximately seventy microliters of serum will be used to measure insulin, glucose, total cholesterol, CCK and CRP using standard techniques.

4.1.7. Gastric Motility

The WMC system (SmartPill Corporation, Buffalo, NY) consists of an indigestible single-use capsule, a receiver, and display software (MotiliGI, SmartPill Corporation) recommended for the assessment of gastric emptying and gut transit time. Also included are assessments of pH, temperature and pressure through the GI tract. This series of studies will be conducted under the direction of gastroenterologist and co-investigator [name], Emory University.

After an overnight fast a representative study meal is consumed and immediately thereafter the participant swallows the SmartPill capsule with an additional 50 ml of water. The participant is then allowed to leave the facility. The participant will resume lunch 5 hours after capsule ingestion. During follow-up the participant records bowel movements, food intake sleep and any GI symptoms. The participant is asked to avoid strenuous exercise, alcohol, smoking and use of any medications that may affect GI motility. The data receiver and diary are returned after 5 days for analysis. Gastric emptying time, small bowel as well as colonic transit time can be estimated by the measuring changes in pH, pressure, and temperature. For example, the movement of the capsule from the stomach to the duodenum results in a pH rises of >3 .⁵⁴

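### The motility capsule's receiver comes back at 5 days whether or not the capsule has exited, and the plan has no way to record or analyse a colonic or whole-gut transit time longer than that

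*Combined protocol and SAP*

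**What the plan says.** Section 4.1.7 describes a system that "consists of an indigestible single-use capsule, a receiver, and display software". The man eats a study meal, swallows the capsule and leaves the facility. "During follow-up the participant records bowel movements, food intake sleep and any GI symptoms". The procedure then closes: "The data receiver and diary are returned after 5 days for analysis". On what is measured, it says: "Gastric emptying time, small bowel as well as colonic transit time can be estimated by the measuring changes in pH, pressure, and temperature".

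Secondary objective 5 (Section 1.1.2) is to "Compare the effects of the high-legume and control diets on gastric emptying time and gut transit time". Section 4.2 singles out the colonic part: "we are now able to examine one of these proposed mechanisms—colon transit time". For the analysis, Section 4.2 states the intent-to-treat principle and "comparisons between treatment groups by two-sample t-tests", with results shown as means and standard errors.

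No section says how exit is verified, how a capsule still inside at receiver return is recorded, or how a transit time longer than the recording is analysed.

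**The concern.** Colonic and whole-gut transit both end when the capsule leaves the body. If recording stops on a fixed day, a man slower than that day has a time known only to exceed 120 h. A t-test cannot use such a value, so the likely default is to leave him out.

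The values lost this way are by construction the longest. If one diet gives longer transit than the other, the slower arm loses more of its upper tail, and the difference among the remaining men is smaller than the true one. With 7 men per arm, one lost extreme value is a visible part of the data on a mechanism that the protocol is keen to examine.

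The same gap leaves no written step at which anyone establishes that the capsule has passed.

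**Working it through.** **The plan's own figures.** There is none for transit. The only sample-size figure (Section 4.2: 5 per arm, 1.25 kg, SD 0.7 kg, 80% power) concerns weight loss. It reproduces under a normal approximation, Φ(1.25/(0.7·√(2/5)) − 1.96) = Φ(0.863) = 0.806, but does not bear on this point.

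**Inputs from the documents.** Recording window 5 × 24 = 120 h (Section 4.1.7); 7 men per arm, 14 in all, and t-tests between arms (Section 4.2).

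**Assumptions, because the documents are silent.** Transit is log-normal with median m and log-SD σ. The legume median is r times the control median. Men with no exit by 120 h are dropped. One comparison between arms is made.

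**Formulas.** With b = (ln 120 − ln m)/σ:
- share beyond the window: p = 1 − Φ(b)
- true mean: m·exp(σ²/2)
- mean among men who exit in time: m·exp(σ²/2)·Φ(b − σ)/Φ(b)
- chance that at least one of 14 has no value: 1 − (1 − p_C)^7·(1 − p_L)^7

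**Worked case.** Control median 60 h, σ = 0.6, r = 0.8, so the legume median is 48 h.
- Control: b = ln(120/60)/0.6 = 1.155, p = 12.4%. Legume: b = ln(120/48)/0.6 = 1.527, p = 6.3%.
- True means are 71.8 and 57.5 h, a difference of 14.4 h. Means among men with an exit are 58.3 and 50.5 h, a difference of 7.8 h.
- Chance of at least one affected man: 1 − 0.876^7 × 0.937^7 = 75%.

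**Same model, three control medians (σ = 0.6, r = 0.8).**

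| Control median | Beyond 120 h, control / legume | At least 1 of 14 | True difference | After dropping |
|---|---|---|---|---|
| 40 h | 3.4% / 1.4% | 29% | 9.6 h | 7.4 h |
| 60 h | 12.4% / 6.3% | 75% | 14.4 h | 7.8 h |
| 72 h | 19.7% / 11.1% | 91% | 17.2 h | 7.5 h |

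**Either direction, legume minus control, indexed by the control share beyond 120 h (σ = 0.5).**

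| Control share | r = 0.8: true → after dropping | r = 1.25: true → after dropping |
|---|---|---|
| 1% | −8.5 → −7.8 h | +10.6 → +8.7 h |
| 5% | −11.9 → −9.0 h | +14.9 → +9.0 h |
| 20% | −17.9 → −8.5 h | +22.3 → +7.5 h |

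With σ = 0.7 the extremes are −6.0 → −5.3 h (1%, r = 0.8) and +21.3 → +6.2 h (20%, r = 1.25). Over both σ and both directions, the loss is about 8-20% at 1%, 24-44% at 5% and 52-71% at 20%. With r = 1 the difference is 0 before and after.

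**Chance of any affected man if both arms share a fraction f:** 1 − (1 − f)^14 = 13%, 25%, 51%, 77% and 96% for f = 1%, 2%, 5%, 10% and 20%.

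**Standardised effect.** Dropping the slowest men also shrinks the SD. In the first table's model the difference divided by the SD is 0.336 without dropping, and 0.331, 0.305 and 0.288 with it. The largest loss is 1 − 0.288/0.336 = 14%. By 2(1.96 + 0.842)²/d², a later trial would need about 139 per arm without dropping, and about 143, 169 and 190 with it.

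**The case against.** The strongest reply is that nothing in the documents shows that any man will exceed 120 h. The medians above are assumed. At 40 h the expected number is 7 × 0.034 + 7 × 0.014 = 0.33 of 14. The plan also states intent-to-treat and nowhere says that men without a value will be dropped. That stands, and it is why the bias is conditional. It needs exits after 120 h, a true diet effect and omission of the affected men. A reader might infer that the transit comparison is biased as planned; the documents do not support that.

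A reader might also infer that a capsule not yet passed would escape attention. The documents do not support that either. The temperature signal and diary can show an exit within the 5 days, a gastroenterologist directs the tests, food pick-up visits are weekly (Section 3.1.2), and twice-weekly calls ask about gut symptoms (Section 4.1.4). None of these is a check of capsule exit, however, and a receiver already returned cannot show a later one.

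Nor do the documents support inferring that the pilot would mis-size a later trial. In the case computed, the standardised effect falls by at most 14%, and the error leads to a larger trial, not an underpowered one. In the pilot itself, the hours lost in the first table (about 2, 7 and 10) are below the standard errors of the difference without dropping (about 15, 23 and 27 h).

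Finally, the documents state no direction for colonic transit. Sections 1.2.8 and 4.2 speak of slower gastric emptying, which is a different segment. This changes which arm loses more men, but not the pull toward zero.

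**Conclusion.** The point holds as a gap in recording and analysis. Recording stops at 5 days regardless of exit. A colonic or whole-gut time beyond 120 h would have no usable value, and the planned t-test cannot take a censored one. Dropping such men can bias a real diet difference toward zero.

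The size cannot be fixed from the documents. Under log-normal times with log-SD 0.5-0.7 and a diet ratio of 0.8 or 1.25, the loss in hours runs from under a tenth when 1% of control men are that slow to more than half when 20% are. It is zero when the diets do not differ.

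The scope is limited. Gastric emptying, the other half of objective 5, needs only that the capsule leaves the stomach. Small-bowel time likewise does not need exit. Section 1.1 lists emptying and transit among the exploratory analyses, and the weight endpoint is untouched. The change is still worth making, because the data needed are already collected and the present test cannot use the affected values.

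**What to change.** In Section 4.1.7, state that staff read exit status from the temperature trace and the bowel-movement diary when the receiver is returned. Any unconfirmed exit goes to the gastroenterologist co-investigator who already directs these tests. The clinical handling is for that investigator to specify.

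In Section 4.2, state that a transit time without recorded exit is right-censored at receiver return (>120 h), not missing. Compare colonic and whole-gut transit between arms by a rank test with censored values ranked highest. If return times differ between men, use a time-to-event method instead. Report the number of non-exits per arm, and medians in place of means for these two outcomes. The gastric emptying analysis can stay as planned.

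The cost is a few lines of protocol text, a few minutes per recording and an occasional referral, with no extra procedures or staff. The small downside is that the transit comparison is no longer a difference in means.
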